Use of Extended Platelet-Rich Fibrin Membranes in Comparison to Collagen Membranes for Socket Grafting: Part 2: A Randomized Clinical Trial

Unique Protocol ID: 13180-[name]

Date of Document: 2/2/2025

Principal Investigator: [name]

Brief Title: E-PRF vs Collagen Membranes in Ridge Preservation

Secondary IDs: None

Study Protocol:

Abstract

Dental implants are often considered the gold standard to replace missing teeth. Having success with dental implants depends on the hard tissue and soft tissue remaining after tooth extractions. The first step to successful dental implant placement begins with proper socket grafting which includes placing a bone graft and membrane among other biomaterials such as platelet-rich fibrin (PRF) to prevent the collapse of the ridge that occurs after a dental extraction.

While platelet-rich fibrin is commonly utilized for ridge preservation, it is often used in conjunction with a collagen membrane due to the fact that it has a short resorption time lasting roughly 2 weeks. However, recently, it was discovered that by heating the plasma layer and denaturing the albumin, the resorption properties of PRF could be extended from 2 weeks to 4-6 months. This extended platelet-rich fibrin (e-PRF) membrane is a promising replacement to collagen membranes in various surgeries. The investigators previously demonstrated that it is a safe and feasible alternative to conventional membranes with 4 different iterations of applying the novel e-PRF membrane. However, there still lacks a comparative study to traditional collagen membranes and between the 4 different iterations.

Objective

The purpose of this study is to evaluate and compare the effectiveness of 4 different iterations of utilizing e-PRF membranes with a collagen resorbable membrane. Each placement will receive either one of the 4 different variations of e-PRF membranes or a collagen resorbable membrane in alveolar ridge augmentation.

Project Design

This research will be a 6-month randomized and controlled trial involving patients requiring at least one extraction and replacement with a dental implant. Participants will be recruited and randomly allocated to receive either one of the four iterations of using e-PRF membranes or a standard resorbable collagen membrane. All patients will be treated surgically with ridge preservation and dental implant placement using standard bone graft material and one of the membranes determined by their assigned group.

Background Information and Scientific Rationale

Dental implants are often considered the gold standard to replace missing teeth. Having success with dental implants depends on the hard tissue and soft tissue remaining after tooth extractions.

¹ The first step to successful dental implant placement begins with proper socket grafting which includes placing a bone graft and membrane among other biomaterials such as platelet-rich fibrin (PRF) to prevent the collapse of the ridge that occurs after a dental extraction.

While platelet-rich fibrin is commonly utilized for ridge preservation, it is often used in conjunction with a collagen membrane due to the fact that it has a short resorption time lasting roughly 2 weeks.²⁻⁴ However, recently, it was discovered that by heating the plasma layer and denaturing the albumin, the resorption properties of PRF could be extended from 2 weeks to 4-6 months. This extended platelet-rich fibrin (e-PRF) membrane is a promising replacement to collagen

membranes in various surgeries. The investigators previously demonstrated that it is a safe and feasible alternative to conventional membranes with 4 different iterations of applying the novel e-PRF membrane.^{5, 6} However, there still lacks a comparative study to traditional collagen membranes and between the 4 different iterations.

Four different techniques utilizing e-PRF membranes for ridge augmentation will be performed with a collagen membrane as a control group. These techniques include 1) e-PRF as a sole barrier membrane, 2) layering a solid-PRF membrane over the e-PRF membrane, 3) fabricating e-PRF intra-orally in gel form as a Bio-Filler, and 4) Fabricating the e-PRF membrane intra-orally under a solid-PRF membrane.

Participant Selection

Participants will receive comprehensive information regarding the treatment procedure, materials utilized, and potential risks or complications to ensure full understanding. This research will encompass a comprehensive and inclusive patient selection process to ensure a diverse and representative sample. Eligible participants will be adults aged 18-75 requiring at least one extraction and replacement with a dental implant. Efforts will be made to include individuals from various racial, ethnic, and socioeconomic backgrounds, as well as different genders.

Exclusion criteria will be carefully defined to maintain the study's integrity while prioritizing inclusivity. If the subject decides to participate in the study, subjects will be given ample time to review the consent form and ask any questions before signing. Subjects will be given a copy of the informed consent for their reference. Participation in the study is entirely voluntary and they can withdraw at any time without penalty.

Inclusion Criteria

- Male and Female subjects aged 18-75 requiring at least one extraction and replacement with a dental implant.
- No contraindications to dental implant placement

Exclusion Criteria

- Smokers
- Autoimmune disease or disorder
- Neurologic disease or disorder
- Major mechanical obstruction to the mouth opening
- Acute capsulitis
- Bone metabolic disease
- Current systemic antibiotic treatment or within 3 months prior to the study
- Drug addiction or alcohol abuse
- Pregnancy, planning to become pregnant and or nursing
- Type 1 diabetes
- Uncontrolled Type 2 diabetes (Anyone with an A1c $\geq 7\%$)

Enrollment

This single site study is expected to enroll a total of 80-100 subjects.

Data Analysis and Interpretation

All collected data, including personal and medical information, is handled with the highest level of security and confidentiality to uphold the privacy and rights of the participant. The informed consent process, a key component of the protocol, clearly communicates to participants how their data will be treated, emphasizing the commitment to confidentiality. Data collection, storage, and transmission procedures incorporate high-security measures, including encryption and password protection, to prevent unauthorized access. Personally identifiable information is carefully managed, with a focus on anonymization or de-identification wherever possible to minimize the risk of participant identification. The investigators are granted access only on a need-to-know basis, and strict access controls are implemented. Regular monitoring, audits, and compliance checks are conducted to ensure that data confidentiality measures are consistently followed throughout the study, promoting trust among participants and maintaining the integrity of the study. Safeguarding data confidentiality is of utmost importance to uphold the privacy and rights of study participants.

This study will undertake a comprehensive analysis to compare outcomes across 5 distinct treatment groups. The primary focus will be to evaluate differences in ridge dimensions through dental radiology and also to evaluate soft tissue healing and closure at 2 weeks post-operatively. The goal is to draw conclusive findings regarding the healing of extraction sites, soft tissue thickness, and ridge dimensions.

Compensation to Participants

Participants will not receive any type of compensation or payment for their participation in the study.

Adverse Event Reporting

In the case of an adverse event (AE) or severe adverse event (SAE) directly associated with the study, participants will not be financially responsible for any consequences resulting from their participation in the study. Should a serious AE occur, any associated medical expenses or required interventions will be covered by the research team. The investigators are fully committed to providing support and resources to manage and address any unexpected challenges that may arise, reaffirming the investigators commitment to the ethical and responsible conduct of research.

Adverse event reporting aims to ensure participant safety, facilitate the evaluation of the intervention's safety profile, and contribute to the overall understanding of potential risks associated with blood draws and extraction and implant therapy. When an adverse event (AE) or severe adverse event (SAE) occurs, it will be promptly and accurately documented. The AE or SAE will be classified in nature, severity and relation to the procedure. It will be reported to all parties including the regulatory authority and ethics committee. The subject will be closely followed until the AE or SAE has been resolved. Timely and transparent reporting is essential for maintaining the integrity of the study, protecting participant welfare, and informing regulatory decisions to ensure the ongoing safety and efficacy of medical interventions.

Principle Investigator Safety Monitoring

1.) Adverse Event Monitoring:

- a. Evaluation of any adverse events (AEs) or serious adverse events (SAEs), which are unfavorable or unintended medical occurrences, to determine their nature, severity, and relationship to the intervention.

2.) Data Collection and Analysis:

- a. Continuous collection and analysis of safety-related data including participant health status and reported symptoms, to identify any patterns or trends that may indicate safety concerns.
- b. Data collection will take place at each procedure visit

3.) Regular Assessments:

- a. Assessment will be conducted at each visit to monitor for potential side effects, complications, or changes in health status related to the intervention.
- b. Each assessment visit will include a CBCT to assess bone levels and intra-oral photographs to evaluate healing.

4.) Compliance with Protocols:

- a. All treatment protocols will be followed, including adherence to safety procedures and guidelines outlined in ethical standards and regulatory requirements.

5.) Communication:

- a. Clear communication with the principal investigator, research staff, and participants to promptly report and address any safety concerns or adverse events.

6.) Ethical Oversight:

- a. Ethical principles and guidelines will be followed to prioritize participant safety and ensure that the research is conducted with the highest standards of integrity.

7.) Regulatory Reporting:

- a. Reporting and monitoring of any adverse events and safety-related data directly to the institutional review boards (IRB) and all related parties.

8.) Risk-Benefit Assessment:

- a. Continued assessment of the overall risk-benefit profile of the intervention to determine whether the potential benefits outweigh the risks and whether any modifications to the study protocol are necessary.

9.) Documentation:

- a. Through documentation of all safety-related information, including adverse events, their resolution, and any actions taken to address safety concerns.

Data Collection

Ensuring data confidentiality is paramount in a research protocol to protect the privacy of participants and maintain the integrity of the study. The protocol outlines rigorous measures to safeguard all collected data, including personal, medical, and potentially sensitive information related to periodontal disease. Key considerations for data confidentiality in a research protocol include:

Informed Consent Process:

Clearly articulate to participants how their data will be handled, emphasizing the importance of confidentiality during the informed consent process. Verbalize the extent to which their information will be anonymized or de-identified to protect their identity.

Resources Available

This study will be facilitated by [name] and [name], both are trained in GCP, HSR, and HIPPA. Staff is also trained in data collection, documentation, and storage.

Early Withdrawal of Subjects

Ideally, each participant should stay engaged in the study until the mandated follow-up period concludes. Nevertheless, participation in any study is entirely voluntary, and participants retain the right to withdraw at any time without facing penalties or loss of benefits. Possible reasons for discontinuation may encompass but are not restricted to, the following:

- Unacceptable adverse experience
- The subject is lost to follow-up
- Subjects withdraw consent for any reason
- Investigators withdraw in the best interest of the subject(s)
- Replacement of Screen Fails and Early Termination
- Study Termination

For those subjects who discontinue participation early, each subject will be followed for 30 days for adverse event monitoring (serious adverse reactions will be monitored for 90 days) after discontinuation. Monitoring of adverse reactions may be done by telephone at the study site director's discretion.

Interventions

The study will involve the standard ridge preservation procedures in patients requiring at least one extraction and replacement with a dental implant. Data collection will be conducted at each visit. The gathered data will undergo analysis using appropriate statistical methods, with the primary objective of soft tissue thickness, quality of healing, dental implants success rate, and alveolar bone levels after surgical extraction and implant placement following a standardized protocol.

Participants requiring at least one extraction and replacement with a dental implant who wish to participate in this study will have a one of the 5 membrane variations performed during their routine extraction and bone graft. Thus, there will be five treatment groups.

Group 1 (Control): Resorbable Collagen membrane

Group 2: e-PRF as a sole barrier membrane,

Group 3: Layering a solid-PRF membrane over the e-PRF membrane,

Group 4: Fabricating e-PRF intra-orally in gel form as a Bio-Filler, and

Group 5: Fabricating the e-PRF membrane intra-orally under a solid-PRF membrane

Methods

Once patients are placed in their corresponding group, they will undergo ridge preservation surgery using standard bone allograft particulate mixed with PRF and secured with a membrane of their respective group. Radiographic data will be collected at conclusion of the surgery. Soft tissue thickness will be measured at the buccal and lingual aspect of the tooth. At the two-week post-operative evaluation, intra-oral photographs will be taken and sent to 3 blinded clinicians to rate the quality of healing for each case. After 3 months with new radiographic data, patient will be scheduled for implant placement with a second stage implant procedure scheduled 3 months after placement. Patients will be encouraged (but not required) to stay for 1 year after implant uncovering with peri-implant parameters recorded every 6 months.

Therapeutic Material Preparation

Blood will be collected through an aseptic technique. Using a butterfly needle set and vacutainer tubes.

Extraction Protocol

Atraumatic extractions will be completed to preserve socket walls. Complete degranulation will be completed utilizing curettes and a carbide bur on a slow-speed handpiece. After degranulation sockets will be irrigated and packed with sticky bone utilizing c/c allograft and both solid and liquid PRF. The Bio-Heat device will be utilized to heat the patient's plasma and create the various iterations of the e-PRF membrane in the 4 treatment groups, the control group will receive a resorbable collagen membrane. All membranes will be secured with chromic gut in 3-0 mattress fashion.

Implant Placement Protocol

After CBCT evaluation and implant planning, osteotomies for BioHorizons dental implants will be prepared according to manufacturer's instructions. All implants will be placed utilizing a delayed approach placing the implants 0-.5mm subcrestally with primary closure achieved utilizing 3.0 chromic gut. Prior to implant placement, soft tissue measurements will be taken.

Implant Uncovery Protocol

A 15 Blade will be utilized and full thickness flaps reflected to allow access to the implant platform. Any bone growth over top of the implant will be removed with a highspeed diamond round bur. The cover screw will be removed and stock BioHorizons healing abutment placed. 3.0 Chromic sutures will be utilized in single interrupted fashion.

Post-op evaluations and Implant planning

Patients will be seen 2 weeks after each procedure to ensure proper healing and any adverse reactions will be recorded. Intra-oral photographs will also be taken at each visit to evaluate wound

healing. 3-months after ridge preservation, patient will be seen for a radiographic evaluation (CBCT) for proper implant planning.

Re-evaluation treatment (not required)

Patients will be encouraged to return every 6 months after the surgery for data collection including probing depths.

Periodontal Maintenance Treatment

Patients will be placed on a 6-month maintenance with data collection (periodontal charting and fasting blood draw) occurring at each maintenance for up to 1-year after implant placement. Patients will also have supragingival scaling completed with curettes and ultrasonic device completed by a trained study personnel. The first maintenance will begin 6 months after the implant uncovering surgery visit until the 1-year follow-up conclusion of the study. The total study from extraction to final follow-up may last up to 2-years.

Study Timeline

Visit 1 - Screening/Baseline

- Informed Consent
- Medical History
- HIPPA Form
- Urine HCG test if applicable
- Inclusion/Exclusion Criteria
- Periodontal charting
- Necessary Radiographs (CBCT)
- Soft tissue measurements
- Intra-oral photographs

Visit 2- Treatment

- Treatment (Extraction Procedure)
- Intra-oral photographs
- Soft tissue measurement
- Necessary radiographs (CBCT)

Visit 3- Post-operative visit

- 2-week post-operative evaluation after surgical procedure.
- Intraoral photographs

Visit 4- Implant planning appointment

- Necessary Radiographs (CBCT)

Visit 5- Treatment

- Treatment (Implant placement)
- Soft tissue measurements
- Intraoral photographs
- Peri-apical radiographs

Visit 6- Post-operative visit

- 2-week post-operative evaluation after surgical procedure.
- Intraoral photographs

Visit 7- Treatment

- Treatment (implant uncovering appointment)
- Necessary radiographs (CBCT)
- Intraoral photographs

Visit 8- Post-operative visit

- 2-week post-operative evaluation after surgical procedure.

Visit 9 (encouraged)- periodontal maintenance (6 months after implant uncovering)

- Supragingival scaling
- Complete periodontal charting
- Necessary radiographs (CBCT)

Visit 10 (encouraged)- periodontal maintenance (12 months after implant uncovering)

- Supragingival scaling
- Complete periodontal charting
- Necessary radiographs (CBCT)

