Use of Extended Platelet-Rich Fibrin Membranes in Comparison to Collagen Membranes for Socket Grafting: Part 2: A Randomized Clinical Trial

Unique Protocol ID: 13180-[name]

Date of Document: 2/2/2025

Principal Investigator: [name]

Brief Title: E-PRF vs Collagen Membranes in Ridge Preservation

Secondary IDs: None

Statistical analysis Plan for evolution Part 2 study:

The sample size was determined based on the expected mean difference in horizontal ridge width (HRW) between independent groups. A mean difference of 2.3 mm with an estimated standard deviation (SD) of 1.1 mm was used for the calculation. To detect a statistically significant difference at an α level of 0.05 with 90% power, a minimum of 11 participants per group was required. Considering an anticipated 20% dropout rate, the final target sample size was set at 14 participants per group.

All statistical analyses were conducted using GraphPad Prism version 10.0 (GraphPad Software, San Diego, CA, USA). Data were first evaluated for normality utilizing the Shapiro-Wilk test. One-way analysis of variance (ANOVA) was used to identify overall differences among the research groups. When ANOVA showed statistical significance, appropriate post hoc tests were performed. Tukey's multiple comparison test was used to compare all possible pairs of group means in the study, where no single control group was defined (i.e., membranes' fabrication and application time). In contrast, Dunnett's post hoc test was used in the analysis involving a defined control group (i.e., collagen) to specifically compare test groups with the control group while controlling for type I error across multiple comparisons. Results were expressed as mean \pm standard deviation (SD), and statistical significance was set at $p < 0.05$.

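### The SAP plans no confidence interval for e-PRF minus collagen, and it skips that comparison whenever the overall ANOVA is not significant

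*Protocol*

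**What the plan says.** The protocol's Abstract, and again its Background section, state: "This extended platelet-rich fibrin (e-PRF) membrane is a promising replacement to collagen membranes in various surgeries". Both give the lack of a study against collagen as a reason for the trial. The Objective section is worded neutrally: the purpose is to "evaluate and compare the effectiveness of 4 different iterations of utilizing e-PRF membranes with a collagen resorbable membrane".

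The SAP's first paragraph sizes the trial on horizontal ridge width: "A mean difference of 2.3 mm with an estimated standard deviation (SD) of 1.1 mm was used for the calculation". The aim is "To detect a statistically significant difference at an α level of 0.05 with 90% power", for which "a minimum of 11 participants per group was required", and then "Considering an anticipated 20% dropout rate, the final target sample size was set at 14 participants per group". The protocol's Enrollment section gives a different total: "This single site study is expected to enroll a total of 80-100 subjects".

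The SAP's second paragraph starts with a one-way ANOVA and moves to post hoc tests only if it is significant. Where collagen is the control, the post hoc test is Dunnett's, used "to specifically compare test groups with the control group while controlling for type I error across multiple comparisons". Results are expressed as mean and SD, with a 0.05 significance threshold. Neither document mentions a confidence interval, an equivalence or non-inferiority margin, or how a non-significant result will be read.

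**The concern.** A comparison of effectiveness should end with an estimate of how far each e-PRF arm lies from collagen and how uncertain that estimate is. The SAP does not commit to one. Its sequence also drops the comparison with collagen when the overall test is not significant, which is the usual outcome if the membranes perform alike. The planned output would then be five means, five SDs and one overall p-value.

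Because the background presents e-PRF as a possible replacement, such a result could easily be taken as reassurance. Whether it is reassuring depends on how much loss of ridge width the data leave open, and the plan does not ask for that figure.

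**Working it through.** **Inputs.** From the SAP: SD 1.1 mm, design difference 2.3 mm, α 0.05 (taken as two-sided, since sidedness is not stated), 11 evaluable and 14 recruited per group. From the protocol: five groups and 80 to 100 subjects, so 16 to 20 per group if allocation is equal. Assumed: equal arms, normal data and a common SD.

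**The plan's own figure.** The two-group formula gives n = 2(1.960 + 1.282)² × 1.1² / 2.3² = 4.8, so 5 per group, or 6 with the t distribution. The stated inputs therefore do not give 11. The dropout step does reproduce: 11 / 0.8 = 13.75, so 14. The gap at 11 is a separate matter and in the safe direction for a 2.3 mm difference. The sizes below are taken as the documents give them.

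**Precision against collagen.** The standard error of a difference is 1.1 × √(2/n). The simultaneous 95% half-width is c times that, where c is the two-sided Dunnett critical value for four comparisons with 5(n − 1) degrees of freedom (simulated, 1,000,000 draws). The half-width is also the smallest observed difference that Dunnett's test would call significant when the pooled SD is 1.1 mm.

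| Evaluable per group | df | c | SE (mm) | Half-width (mm) |
|---|---|---|---|---|
| 11 | 50 | 2.523 | 0.469 | 1.18 |
| 14 | 65 | 2.501 | 0.416 | 1.04 |
| 16 | 75 | 2.493 | 0.389 | 0.97 |
| 20 | 95 | 2.482 | 0.348 | 0.86 |

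The rows for 16 and 20 are the protocol's enrolment with no dropout. With the SAP's 20% dropout, that enrolment leaves 16 × 0.8 = 12.8 to 20 × 0.8 = 16 per group.

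**How often the comparison would be run.** If all five true means are equal, ANOVA at the 0.05 level is non-significant in 95% of trials by construction, and Dunnett's test is then not performed.

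**Illustration: one e-PRF arm truly 1.0 mm narrower, the other arms equal to collagen.** The 1.0 mm is an assumption; the documents give no clinically important loss. Dunnett alone is computed from the noncentral t. The planned sequence (ANOVA significant, then Dunnett significant for that arm) is simulated with 200,000 trials per size.

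| Evaluable per group | Detected, Dunnett alone | Detected, planned sequence | Missed, planned sequence |
|---|---|---|---|
| 11 | 36% | 32% | 68% |
| 14 | 47% | 43% | 57% |
| 16 | 53% | 50% | 50% |
| 20 | 65% | 63% | 37% |

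If all four e-PRF arms are 1.0 mm narrower, the planned-sequence figures change by less than one percentage point. At the SAP's own 2.3 mm the picture is quite different: at 11 per group 2.3 / 0.469 = 4.90 standard errors against a critical value of 2.52, and Dunnett power is about 99%.

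**What an interval would show.** An observed deficit of 1.0 mm would read −2.18 to +0.18 mm at 11 per group (−1.0 ± 1.18) and −2.04 to +0.04 mm at 14 (−1.0 ± 1.04). Both are non-significant, and both leave open a loss of about 2 mm.

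**The case against.** The strongest reply is that a test of difference fits an objective about difference. The replacement sentence is background and refers to surgeries in general. The remark that e-PRF is a safe and feasible alternative describes what the investigators say they have already shown. The Objective, the Data Analysis section and the Conclusion all speak of comparing or evaluating differences. This stands. A reader might infer that the trial asks whether e-PRF can replace collagen and so should have been a non-inferiority trial; the documents do not set that question. A reader might also infer that the investigators mean to treat a non-significant result as equivalence; neither document says so.

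A second reply is that means and SDs, with group sizes, let a reader rebuild intervals. That is right for unadjusted intervals, so it would be too strong to say the plan gives nothing to judge by. What is missing is the commitment to report the differences with intervals adjusted for four comparisons, and a rule for reading them.

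Third, nothing in the documents makes 1.0 mm clinically relevant. That also stands, and for the 2.3 mm the trial was sized on, power is ample. At 14 evaluable and SD 1.1 mm, a non-significant Dunnett comparison would have a lower limit above −2 × 1.04 = −2.08 mm, which excludes a 2.3 mm loss.

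Fourth, it would be wrong to say that an observed 1.0 mm deficit is always non-significant. At 16 to 20 evaluable per group the threshold is 0.97 to 0.86 mm, so such a deficit would reach Dunnett significance, provided ANOVA were significant first.

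**Conclusion.** The point holds as a cheap improvement to analysis and reporting. It is not a contradiction or an error in the plan. The SAP makes the comparison with collagen conditional on ANOVA and plans no interval, so it gives least information when the arms look alike. With SD 1.1 mm and equal arms, the uncertainty left unreported is about ±1.18 mm at 11 per group, ±1.04 mm at 14, and ±0.97 to ±0.86 mm at 16 to 20.

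The half-widths rest on the SAP's SD and on equal arms. The miss rates rest also on the assumed 1.0 mm deficit and should be quoted only as an illustration. The recommendation depends neither on that figure nor on reading the objective as a replacement question, because a neutral comparison needs an estimate with its uncertainty too.

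**What to change.** In the SAP's analysis paragraph:

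- Report, for each of the four e-PRF arms, the difference from collagen in horizontal ridge width with its Dunnett-adjusted 95% confidence interval, whatever the ANOVA result. Dunnett's procedure controls the family-wise error by itself, so dropping the ANOVA condition here does not inflate it.
- State that p ≥ 0.05 will not be read as equivalence.
- Base any statement that e-PRF is an alternative to collagen on the lower confidence limit, that is, on the largest loss of width the data do not exclude.
- Say which result governs if an interval excludes zero while ANOVA is not significant. In the 1.0 mm illustration at 11 per group this happens in about 36% − 32% = 4% of trials.

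The cost is a few sentences and one further output from a method already planned. No margin and no extra patients are needed. The downside is that a null result will support only a more modest claim.

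### Tooth position and socket wall condition are not handled at entry, allocation or analysis, which costs precision in the ridge-width comparison

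*Protocol*

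**What the plan says.** **Entry.** The Protocol's Inclusion Criteria have two items: "Male and Female subjects aged 18-75 requiring at least one extraction and replacement with a dental implant" and "No contraindications to dental implant placement". The exclusions concern general health, habits, medication and mouth opening. Neither list mentions tooth position, number of roots, jaw or the state of the socket walls. The walls appear only as a surgical aim, under Extraction Protocol: "Atraumatic extractions will be completed to preserve socket walls".

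**Allocation.** Project Design says that participants are allocated at random to one of five groups. No stratification, blocking or minimisation is described.

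**Analysis.** The SAP sizes the trial on horizontal ridge width (difference 2.3 mm, SD 1.1 mm, α 0.05, 90% power, 11 per group, 14 after 20% dropout). It plans a one-way ANOVA, followed by Dunnett's test where collagen is the control. It names no covariate, and it does not say whether ridge width is analysed as an absolute value or as a change.

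**What is available.** The Study Timeline puts a CBCT at Visit 1, before the extraction at Visit 2.

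**The concern.** A single-rooted tooth with intact walls and a molar with a lost buccal plate are both eligible. If ridge width differs between such sites, the difference adds to the residual variance of every comparison between arms. It also means that, in the one trial that is run, an e-PRF arm may hold a visibly different mix of sockets from the collagen arm. The planned analysis has no term to account for that, and nothing requires the mix to be recorded or reported. The stake is lower power than the SAP assumes, and a difference between membranes that is hard to interpret when the arms differ in the sockets treated.

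**Working it through.** **1. The plan's own figure.** With 2.3 mm, SD 1.1 mm, two-sided α 0.05 and 90% power, the normal approximation gives n = 2(1.960 + 1.282)² × 1.1² / 2.3² = 4.8, so 5 per group. The exact t calculation gives 6. The SAP's 11 is not reproduced from its stated inputs; a Bonferroni allowance, which the SAP does not mention, would give 9 (four comparisons) or 10 (ten). The dropout step does reproduce: 11 / 0.8 = 13.75, so 14. At 11 per group the stated inputs give 99.7% power, so the design has slack.

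**2. Chance imbalance.** Inputs:
- five arms (Protocol, Interventions) of 14 (SAP);
- simple randomisation, because nothing else is described;
- a share p of sites of one type, assumed to be 30–50% because the documents give none.

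The count in each arm is Binomial(14, p).

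| Gap from collagen | p = 0.3 | p = 0.4 | p = 0.5 |
|---|---|---|---|
| 4 or more sites, a given e-PRF arm | 15% | 18% | 18% |
| 4 or more sites, at least one of four | 40% | 46% | 48% |
| 5 or more sites, at least one of four | 19% | 24% | 26% |

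Four sites in 14 is 29 percentage points. The Protocol's Enrollment section expects 80–100 subjects, which is 16–20 per arm if the arms are equal. A gap of at least 25 points in at least one e-PRF arm then has probability 46–54% at 16 per arm (4 sites) and 33–41% at 20 per arm (5 sites).

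**3. Precision.** Assume that 1.1 mm is the SD within one site type, that 40% of sites are of the second type, and that the types differ by D in ridge width. The mixed SD is √(1.1² + 0.4 × 0.6 × D²). Power is for 2.3 mm with 11 per arm, from the exact two-sided t-test. The Bonferroni column uses α = 0.05/4 = 0.0125 as a stand-in for Dunnett's test.

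| D (assumed) | SD | Power, α 0.05 | Power, α 0.0125 |
|---|---|---|---|
| 0 mm | 1.10 mm | 99.7% | 98% |
| 1 mm | 1.20 mm | 99% | 95% |
| 2 mm | 1.47 mm | 94% | 81% |
| 3 mm | 1.84 mm | 80% | 58% |

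**4. Steps 2 and 3 are one effect.** With D = 2 mm and 14 per arm, the variance of a difference between two arms is 2 × 1.21/14 + 2 × 0.96/14 = 0.173 + 0.137 = 0.310. The second term is the chance imbalance. The square root, 0.557 mm, equals 1.47 × √(2/14). The imbalance is already inside the larger SD and must not be added to it.

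**5. Validity.** Trials were simulated with no membrane effect, p = 0.4, D = 1, 2 or 3 mm, 11 per arm and no stratification. The one-way ANOVA rejected in 4.8–4.9% of them, and the largest comparison with collagen passed an approximate Dunnett threshold in 4.7–4.9%. The false-positive rate does not rise.

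**The case against.** **Bias.** A reader might infer that imbalance in socket type biases the comparison, or that it would be taken for a membrane effect. The documents do not support that. Allocation is random, and step 5 shows that the error rate holds. A single result can still be awkward to interpret.

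**Worst case.** The 40–48% is the chance for the worst of four comparisons; for a given arm it is 15–18%. Both belong in the account.

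**Meaning of the SD.** The SAP does not say that 1.1 mm is a within-type SD. If it is the overall SD, it already contains the site mix. D can then be at most 1.1/√0.24 = 2.25 mm at a 40% mix, and the planned power is not reduced. The plan then only forgoes a gain: with D = 1 mm, for example, adjustment would bring the SD from 1.1 to about √(1.21 − 0.24) = 0.98 mm. This objection stands as a limit on step 3.

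**Size.** Unadjusted power stays above the planned 90% for D up to 2 mm. That also stands. With an allowance for four comparisons it falls to 81% at 2 mm.

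**Starting width.** CBCTs at Visits 1, 2 and 4 would allow an analysis of change or one adjusted for baseline, which would remove much of a difference in starting width. The SAP specifies neither, and site types may also differ in the change itself.

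**Terminology.** A reader might infer two target populations, because the Objective speaks of "a collagen resorbable membrane in alveolar ridge augmentation" and Project Design says "All patients will be treated surgically with ridge preservation and dental implant placement". The title and the procedures describe one operation: extraction, socket graft and membrane. The wording is an editorial matter and not part of this point. Broad entry appears deliberate, and nothing here requires it to be narrowed.

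**Conclusion.** The point holds as one of precision and interpretability. No site criterion, no described stratification and no model term means that site type is left entirely to chance and to the residual variance. That allocation is unstratified rests on the Protocol's silence, since it never says so outright.

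The size depends on assumptions that the documents cannot settle: the share of each site type, the effect of site type on ridge width, and whether 1.1 mm is a within-type SD. Over the ranges shown, the loss runs from negligible (1 mm) to material (3 mm, or 2 mm once four comparisons are allowed for). The trial's validity is not in question. The case for changing the plan is that the needed information comes from a scan already scheduled before treatment.

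**What to change.** 1. **Index site.** Designate one site per patient before allocation. Patients may need more than one extraction, and the Objective refers to each placement receiving a membrane, so the unit of randomisation is otherwise unclear and one factor could not classify a patient with two different sockets.
2. **Site factor.** Record one pre-specified binary factor for that site from the Visit 1 CBCT, for example molar versus non-molar.
3. **Model.** Replace the one-way ANOVA for ridge width with a linear model containing arm and that factor, with Dunnett comparisons against collagen on the adjusted means. Confirm that the software named in the SAP can produce these.
4. **Allocation.** If allocation has not started, also stratify the list by the factor, using concealed blocks of randomly varied size (5 and 10). Fixed blocks of five would make the last assignment in each block predictable to an operator who sees every membrane placed. If allocation has started, steps 2 and 3 still recover much of the precision, since the factor can be read from the existing Visit 1 scans without knowledge of the assigned arm.

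The cost is one data field, one model term, a second allocation list and possibly one incomplete block per stratum. No patient is excluded, and no visit, scan or patient is added.
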